6.4 Visit 4/5

Follow-up visits will be required three weeks (± 1 week) and three months (± 2 weeks) after treatment to assess long-term safety, amyloid plaque load and cognitive function through behavioral tests. Two follow-up PET/CT scan using Amyvid (¹⁸F-Florbetapir) will be performed; one 3 weeks (± 1 week) post-FUS and one 3 months (± 2 weeks) post-FUS, to test for potential reduction in the amyloid plaque load. A blood sample will be also collected through an intravenous catheter or a finger prick, to test for long-term changes in blood chemistry and cell count. One follow-up visit following a single FUS treatment was deemed sufficient by the attending neurologist.

7 Statistical Plan

7.1 Sample Size Determination

Successful methodology will be concluded if the BBB opening is safely opened in the PFC region in at least 75% of the cases as evidenced on MRI. The scan with the BBB opening will be compared to the scan before BBB opening for each patient. The data will be statistically analyzed with parametric paired Student's t-test. Power analysis shows that for a detectable difference of 200 mm³ (after BBB opening - before BBB opening) and a standard deviation of 50 mm³, at least 6 subjects are needed to report a result at the level of α =0.05 and Power=0.95.

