5.3 Allocation to Treatment

This is a single arm, non-random trial.

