7.2 Statistical Methods

Standard statistical methods will be used in this study. Parametric analysis will most likely be applied to compare the gadolinium enhancement in the patient's brain before and after BBB opening through paired Student's t-test. However, the statistical analysis will be subject to the results obtained and other methods may be used as well, such as non-parametric statistical tests.

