7.3 Subject Population(s) for Analysis

Protocol-compliant population: Any subject who was randomized and received the study device and complied with all protocol required processing

8 Safety and Adverse Events

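### The success rule in 7.1 is a proportion of safe openings (at least 5 of 6), but the only named test and power figure concern mean enhancement volume, and the stated power does not fit its own inputs

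*Combined protocol and SAP*

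**What the plan says.** All references are to the combined protocol and SAP.

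- **Success rule (7.1).** "Successful methodology will be concluded if the BBB opening is safely opened in the PFC region in at least 75% of the cases", judged on MRI by comparing each patient's scan after opening with the scan before it.
- **Test (7.1).** "The data will be statistically analyzed with parametric paired Student's t-test".
- **Sample size (7.1).** "Power analysis shows that for a detectable difference of 200" mm³ (after minus before) and an SD of 50 mm³, "at least 6 subjects are needed to report a result at the level of" α = 0.05 with power 0.95.
- **Methods (7.2).** The expected analysis would "compare the gadolinium enhancement in the patient's brain before and after BBB opening through paired Student's t-test". The choice of method is then left open, because "the statistical analysis will be subject to the results obtained and other methods may be used as well", with non-parametric tests as the only example.
- **Analysis set (7.3).** One population is defined: "Any subject who was randomized and received the study device and complied with all protocol required processing".
- **Allocation (5.3).** "This is a single arm, non-random trial".
- **Scans (3.1, 6.1, 6.2).** The planning MRI is acquired without gadolinium. The same-day MRI after sonication is acquired both with and without it. Section 5.7 names the contralateral site as the comparison for safety and effectiveness.
- **Objectives.** Safety and feasibility are primary (2.1). Defining the success rate at the chosen settings is secondary (2.2).

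**The concern.** The rule that decides the trial is a count of subjects, and each must satisfy two conditions: the barrier opened, and opened safely. The planned test is about a different quantity, the average volume change, in which safety plays no part. A significant mean change does not show that 75% of subjects opened, and meeting the 75% rule does not depend on the t-test.

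Three further gaps follow. A reader could take the 0.95 power as the chance that the trial succeeds, which it is not. The denominator of the proportion can shift, because the only defined population excludes non-compliant subjects and is worded for a randomized trial. The before/after gadolinium comparison has no gadolinium scan on the before side.

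What is at stake is how six results are read. As written, the decisive fraction would be reported without an interval or known operating characteristics, beside a p-value that answers another question.

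**Working it through.** **Inputs.** N = 6 (3.1, 6). Success at 75% or more (7.1). Difference 200 mm³, SD 50 mm³, α 0.05, power 0.95 (7.1). Assumptions: two-sided test, since sidedness is not stated; one case per subject. The plan does not say whether 50 is the SD of the paired difference or of each scan, so both are tried.

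**1. The plan's own figure.** Paired t-test power = P(T > t(0.975, n−1)), where T is noncentral t with n−1 degrees of freedom and noncentrality (200/SD of the difference) × √n.

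| SD of difference | n | Critical t | Noncentrality | Power |
|---|---|---|---|---|
| 50 | 3 | 4.303 | 4 × √3 = 6.93 | 0.908 |
| 50 | 4 | 3.182 | 4 × √4 = 8.00 | 0.998 |
| 50 | 6 | 2.571 | 4 × √6 = 9.80 | > 0.9999 |
| 70.7 | 3 | 4.303 | 2.83 × √3 = 4.90 | 0.705 |
| 70.7 | 4 | 3.182 | 2.83 × √4 = 5.66 | 0.950 |
| 70.7 | 6 | 2.571 | 2.83 × √6 = 6.93 | 0.9996 |

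The 70.7 rows take 50 as the per-scan SD with zero correlation: 50 × √2 = 70.7. On either reading four subjects reach 0.95. For six subjects to give exactly 0.95, the SD of the difference would have to be about 107 mm³ (200/1.867).

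**2. The rule as a count.** 0.75 × 6 = 4.5, so at least 5 of 6; 4/6 is 67%. P(at least 5 of 6) = 6p⁵(1−p) + p⁶, where p is the true rate of safe opening.

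| p | 6p⁵(1−p) | p⁶ | P(rule met) |
|---|---|---|---|
| 0.50 | 0.094 | 0.016 | 0.11 |
| 0.60 | 0.187 | 0.047 | 0.23 |
| 0.75 | 0.356 | 0.178 | 0.53 |
| 0.90 | 0.354 | 0.531 | 0.89 |

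A 95% chance of meeting the rule needs p of about 0.94.

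**3. What the count can support.** Clopper-Pearson 95% limits: 5/6 gives 35.9% to 99.6%; 6/6 gives 54.1% to 100%. Even six out of six does not exclude rates below 75%.

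**4. Test and rule can disagree.** Illustration with assumed changes of 200, 200, 200, 200, 0 and 0 mm³: mean 133, SD 103, t = 133.3/(103.3/√6) = 3.16 on 5 df, two-sided p = 0.025. The test is significant, but only 4 of 6 opened and the rule is missed.

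**5. Denominator.** With four safe openings among six treated, 4/6 = 67% and the rule is missed. If one of the two failures is set aside as non-compliant under 7.3, 4/5 = 80% and the rule is met.

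**6. Baseline.** Section 7.2 compares gadolinium enhancement before and after. The before scan (3.1, 6.1) has no gadolinium, so the two sides are not the same measurement.

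**The case against.** A six-patient, single-arm feasibility study needs no hypothesis test of a proportion. Section 7.1 says how each case is judged: on MRI, by a per-patient scan comparison. Safety has named tools in 3.4 and listed events in 8.5. Section 8.5 also counts by subject: failure to open in three subjects leads to contact with the FDA. The plain denominator is six, and the reference to randomization in 7.3 looks like template text. The power error is on the safe side. The disagreement example uses an SD about twice the planned one. If individual changes were normal with mean 200 and SD 50 (an assumption), an opening threshold of 100 mm³ would be met in at least 5 of 6 with probability 0.993 (0.925 with SD 70.7).

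Much of this stands. A count can be reported without a test, per-patient judging is specified, and the power error does not weaken the study. The example shows only that disagreement is possible. But the 0.993 covers opening and not safety, and it depends on a threshold the documents do not give. The 8.5 trigger also ignores safety, and two failures already miss 75% without reaching it. Even with the word on randomization struck from 7.3, the restriction to compliant subjects remains.

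Some stronger readings are tempting but unsupported:

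- **The t-test replaces the 75% rule.** The plan never says so.
- **Safety goes unassessed.** Sections 3.4 and 8.5 show otherwise.
- **Nobody can be analysed.** This takes one word in 7.3 too literally, given 5.3.
- **The success rate is the trial's main question.** It is a secondary objective (2.2).
- **Fewer than six should be enrolled.** The count, not the volume test, is what six subjects limit.

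**Conclusion.** The point holds and should be fixed. The success rule and the planned inference address different quantities: the t-test and its power say nothing about the proportion of safe openings, and the chance of meeting the rule is 0.53 at a true rate of 0.75, not 0.95. The claim that at least six subjects are needed for power 0.95 is wrong on its stated inputs, which need four and give more than 0.999 at six. The compliant-only population can reverse the outcome (4/6 against 4/5), and the gadolinium comparison lacks a matching baseline.

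These figures assume a two-sided test, one case per subject and six treated subjects; the 0.9996 and 0.950 values also assume a per-scan SD of 50 with zero correlation. The missing per-subject threshold for opened, and the missing list of findings that count against safely, are supporting detail and not the core error.

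**What to change.** 1. **Primary analysis (7.1).** Use the number of subjects with safe opening among all treated subjects. State the rule as at least 5 of 6, and report the result with its Clopper-Pearson 95% interval. Present it as a go/no-go decision, not as proof of a 75% rate.
2. **Population (7.3).** Replace the current definition with all treated subjects.
3. **Volume comparison (7.2).** Make it secondary, with a comparator the trial already acquires: the contralateral site named in 5.7, or the same-session scan without gadolinium. Remove the clause that makes the method depend on the results.
4. **Power (7.1).** Restate it as above 0.999 at n=6 on the stated inputs, or correct the inputs. Keep n=6.
5. **Supporting definitions.** Before the first treatment, the sponsor should fix the per-subject threshold for opened and say which findings count against safely.

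Cost: revised wording in 7.1 to 7.3 and one endpoint definition, with no extra patients or scans. The change needs IRB and possibly FDA submission. The documents offer no ready mm³ threshold, so the sponsor must justify one. A wide interval replaces a p-value as the headline.

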3.4 Primary Safety Endpoints

Safety of the technique will be assessed by MRI and neurocognitive tests, to guarantee that FUS-induced BBB opening at low frequency and pressure does not cause adverse effects in patients.

4 Subject Selection and Withdrawal

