8.2 Recording of Adverse Device Effects

All observed or volunteered adverse effects (serious or non-serious) and abnormal test findings, regardless of treatment group, if applicable, or suspected causal relationship to the investigational device or, if

applicable, other study treatment or diagnostic product(s) will be recorded in the subjects' case histories. For all adverse effects, sufficient information will be pursued and/or obtained so as to permit 1) an adequate determination of the outcome of the effect (i.e., whether the effect should be classified as a serious adverse effect) and; 2) an assessment of the causal relationship between the adverse effect and the investigational device or, if applicable, the other study treatment or diagnostic product(s).

Adverse effects or abnormal test findings felt to be associated with the investigational device or, if applicable, other study treatment or diagnostic product(s) will be followed until the effect (or its sequelae) or the abnormal test finding resolves or stabilizes at a level acceptable to the sponsor-investigator.

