8.5 Stopping Rules

Redundant safety features have been added to the hardware of the device, as grounding for the transducer, safety switch for the amplifier and function generator. Additionally, we will incorporate safety valves in our software. For any signs showing safety risk including high cavitation dose in the acoustic monitoring or unstable vital signs, the device can be stopped from the computer user interface and/or an emergency stop button. Treatment will be stopped in the case of any reaction of the subject to the ultrasound exposure or microbubble infusion. Pulse oximetry will be used during MRI scans to mitigate the risk of anaphylactic reaction to MRI contrast agents. Potential adverse effects have been grouped according to their severity in the following table:

Severity	Adverse effect			
Severe	Local hemorrhage	Edema	Intracranial infection	Status epilepticus
Moderate	Emesis	Dizziness	Allergic reaction	Nausea
Mild	Skull heating	Injection site bruising	Headache	

The investigation will be paused and the relevant authorities will be notified in case of any death, life threatening event, or any other serious adverse event described in the table above (including disability or clinically significant manifestation of local hemorrhage or edema) due to the procedure. An episode of status epilepticus during treatment will terminate the session immediately.

If the selected ultrasound settings (i.e., MI of 0.4) do not successfully open the BBB in 3 subjects, FDA will be contacted via a submission of an IDE supplement, to discuss revising the protocol's focused ultrasound parameters or increase the number of subjects.

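### The 75% success rule does not use recorded adverse effects or fix its denominator, so a subject with a serious procedure-related event could count as a success or drop out

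*Combined protocol and SAP*

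**What the plan says.** The plan has one success rule, in 7.1: the barrier must be "safely opened in the PFC region in at least 75% of the cases as evidenced on MRI". Nothing there says what makes an individual opening safe. For the analysis, 7.2 says "Parametric analysis will most likely be applied to compare the gadolinium enhancement" before and after the procedure, and leaves room for other tests; it describes no safety analysis.

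The primary safety endpoint in 3.4 reads "Safety of the technique will be assessed by MRI and neurocognitive tests". Its stated aim is broader, namely to show that the procedure "does not cause adverse effects in patients". It gives no criterion for a single subject.

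Clinical events are collected. Under 8.2, "All observed or volunteered adverse effects (serious or non-serious) and abnormal test findings" go into the case histories, with enough detail to judge seriousness and causality. Conduct rules follow. In 8.5, "Treatment will be stopped in the case of any reaction of the subject to the ultrasound exposure or microbubble infusion", and "The investigation will be paused and the relevant authorities will be notified in case of any death", a provision that extends to life-threatening and other serious events due to the procedure. Sections 8.6 and 8.6.1 add that the study is discontinued on a reaction to the therapy, and 8.6 withdraws subjects for certain findings.

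The only analysis population, in 7.3, is subjects who "received the study device and complied with all protocol required processing". There is no all-treated or safety population, and 7.1 does not say which population its cases come from.

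**The concern.** Safety is half of the primary objective in 2.1, and the success statement claims safe opening, not just opening. The information needed to judge clinical safety is collected under 8.2, but no sentence carries it into the 75% rule.

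Two gaps follow. The first is the numerator. Some of the events that the protocol anticipates need leave no sign on MRI: status epilepticus and allergic reaction (8.5), and cardiopulmonary reactions to the microbubbles (1.5.1). If safety is judged on MRI, a subject with such an event and a clean scan is a success.

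The second is the denominator. A sonicated subject whose session is cut short under 8.5, or who is withdrawn under 8.6 and then misses required procedures, may no longer meet the 7.3 definition and may not be scored at all.

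At stake is the declared result. The secondary objective in 2.2 is to define the success rate at these ultrasound settings for use in later studies, so that rate will be carried forward.

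**Working it through.** **Inputs.** Six subjects (3.1 and 6); a 75% threshold (7.1). The plan gives no serious-event rates, so the cases below are counts and not probabilities.

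**The plan's own figure.** Section 7.1 justifies six subjects by a paired t-test with a difference of 200 mm³, SD 50 mm³, alpha 0.05 and power 0.95. If 50 mm³ is the SD of the paired difference, the standardised difference is 200/50 = 4. Exact two-sided power is then 0.909 at n = 3 and 0.998 at n = 4, so six is enough. The test concerns opening volume and has no safety component, so the sample size is not affected by this point.

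**Threshold in subjects.** 0.75 × 6 = 4.5, so at least 5 of 6. 0.75 × 5 = 3.75, so at least 4 of 5. 0.75 × 4 = 3, so at least 3 of 4.

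**Three ways to score.** Let n be the number sonicated, m the number opened with a clean MRI, and e the number of those m with a serious procedure-related event.

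- MRI only: m/n
- Affected subjects dropped under 7.3: (m − e)/(n − e)
- Affected subjects counted as not safe, all sonicated in the denominator: (m − e)/n

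| n, m, e | MRI only | Dropped | Counted as not safe |
|---|---|---|---|
| 6, 5, 1 | 5/6 = 83%, success | 4/5 = 80%, success | 4/6 = 67%, not success |
| 6, 6, 1 | 6/6 = 100%, success | 5/5 = 100%, success | 5/6 = 83%, success |
| 6, 6, 2 | 6/6 = 100%, success | 4/4 = 100%, success | 4/6 = 67%, not success |

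The dropped column assumes that the event also led to a missed required procedure; the event alone would not exclude the subject.

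**Early stop.** Suppose the study ends after subject k, all k opened, and the event was in subject k. MRI scoring gives k/k = 100%. Counting the event gives (k − 1)/k, which is 0%, 50%, 67%, 75% and 80% for k = 1 to 5. The two scorings disagree for k = 1 to 3 and agree for k = 4 and 5. The plan does not say whether the rule is applied after an early stop.

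**The case against.** The strongest reply is that the harmful scoring is a strained reading. Section 7.1 asks for safe opening, and the MRI phrase can be taken to attach only to the opening, which only imaging can show. Section 3.4 states its aim in terms of adverse effects, and 8.5 classes status epilepticus as severe. A sensible investigator would not call such a subject safely opened. This stands in part: the text is ambiguous and does not require the bad scoring. But if the MRI phrase covers only the opening, *safely* has no definition at all, and the 8.2 data still do not enter the rule.

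The second reply is that the conduct rules nearly foreclose the lead case. A reaction stops treatment, a stopped session may not open the barrier, and the study is paused or discontinued. The 5/6 against 4/6 contrast needs one other subject who did not open, and an event in the last subject or a study that resumed or had already treated the rest. This also stands, and it is why the point is minor. These rules govern what happens next, however, not how the subject is scored.

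The third reply concerns 7.3. A reader might infer that any adverse effect removes a subject from the analysis. The documents do not say that: 7.3 turns on compliance, and stopping a session under 8.5 follows the protocol. Exclusion arises only if required procedures are missed.

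Finally, with six subjects every serious event would be recorded, reported and visible individually. That is true, and it limits the harm. It does not settle what the declared rate should be.

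**Conclusion.** The point holds as a minor one. The success rule and the primary safety endpoint make no use of the adverse effects recorded under 8.2, and the only stated population can omit a sonicated subject who misses required procedures. With 5 of 6 opened and one of those five affected, the conclusion is success at 83% or 80%, or not success at 67%, and the plan does not choose. With all six opened, one event changes nothing and two events do.

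This assumes a serious procedure-related event that leaves no MRI sign in a subject whose barrier opened and, for the 80% figure, a missed required procedure as well. How likely that is cannot be judged from the documents, so no probability of a wrong conclusion is claimed.

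A reader might go further and infer that the plan disregards adverse events or leaves subjects unprotected. The documents do not support that: 8.2 records all of them, 8.3.2 reports them, and 8.5, 8.6 and 8.6.1 act on them. The gap is in how success is scored.

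**What to change.** - **7.1, denominator.** Apply the 75% rule to all sonicated subjects, whatever their status under 7.3, and also if the study stops early.
- **7.1, definition.** Count a subject as safely opened only if the prefrontal opening is seen on MRI and, through the 3-month visit, there is no procedure-related event that is serious under 8.1 or that triggers the pause in 8.5.
- **3.4.** Add the procedure-related adverse effects recorded under 8.2 to the safety endpoint. The MRI and neurocognitive assessments stay as they are; the new criterion adds to them and relaxes neither.
- **Reporting.** Give the number opened and the number safely opened side by side, so that technical feasibility can still be read separately.

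The cost is rewording. The data are already collected and the 3-month visit is already scheduled, so no new procedures or staff are needed. The downside is that the declared success rate may be lower.

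### The power of 0.95 in section 7.1 does not follow from the paired t-test it names, and its inputs leave almost no room for subjects whose barrier does not open

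*Combined protocol and SAP*

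**What the plan says.** Section 7.1 holds two separate statements.

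- **Success rule.** The method succeeds if the barrier is "safely opened in the PFC region in at least 75% of the cases as evidenced on MRI". With six subjects, 75% is 4.5, so at least five must open.
- **Power statement.** "The scan with the BBB opening will be compared to the scan before BBB opening for each patient". The named test is explicit: "The data will be statistically analyzed with parametric paired Student's t-test". The calculation is made "for a detectable difference of 200 mm³ (after BBB opening - before BBB opening) and a standard deviation of 50 mm³", and the conclusion is that "at least 6 subjects are needed to report a result" "at the level of α =0.05 and Power=0.95".

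The section does not say whether the test is one- or two-sided, where the 50 mm³ comes from, whether it is the SD of the paired difference or of each scan, or whether it describes openers only or all treated subjects. It assumes no opening rate.

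Four other sections bear on the point. Sections 1.5.1 and 2.2 report opening in every animal at a mechanical index of 0.4. Section 2.2 makes the human success rate something for this study to establish. Section 8.5 foresees failure to open in three subjects and says what then happens. Section 7.2 keeps the paired t-test as the likely method but leaves room for others.

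**The concern.** A difference of 200 mm³ with an SD of 50 mm³ is a standardised effect of 4, which is very large. Six subjects should then give far more power than 0.95, so the stated figure looked as if it belonged to another test.

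The inputs also looked too tight. A subject whose barrier does not open contributes about 0 mm³. Even one such subject in six pulls the mean down and spreads the differences widely. The same paragraph allows for some non-opening in its success rule, but the power statement is silent on it.

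At stake is whether the stated power describes the study as it will be run. A reader would take 0.95 as a property of the design. It is neither the power under the plan's own inputs nor a value tied to any stated opening rate.

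**Working it through.** **Inputs from section 7.1:** paired t-test; mean difference 200 mm³; SD 50 mm³; n = 6; alpha 0.05; power 0.95. **Assumed, because not stated:** two-sided alpha (one-sided also shown), and 50 mm³ as the SD of the paired difference.

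**Step 1. Reproduce the plan's figure.** Standardised effect d = 200/50 = 4. Power comes from the noncentral t distribution with n − 1 degrees of freedom and noncentrality d√n.

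| Reading | Result |
|---|---|
| Paired, two-sided | 0.908 at n=3; 0.998 at n=4; above 0.999 at n=6 |
| Paired, one-sided | 0.991 at n=3 |
| Paired, 50 mm³ per scan, zero correlation (d = 200/70.7 = 2.83), two-sided | 0.950 at n=4; above 0.999 at n=6 |
| Two-sample t-test, 3 per group (6 in total), two-sided | 0.948 |

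No paired reading gives 0.95 at six subjects. A paired two-sided test would have power 0.95 at n=6 only if d were 1.867, that is, an SD of 200/1.867 = 107 mm³. The two-sample reading matches both stated figures, but it is not the named test. The documents do not say that it was used.

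**Step 2. How many non-openers do the inputs allow?** Let a fraction q have difference 0 and let the mean over all subjects be 200. The openers then average 200/(1 − q), and even if they were all identical the variance would be q/(1 − q) × 200². Setting this to at most 50² gives q/(1 − q) ≤ 2,500/40,000 = 0.0625, so q ≤ 0.0625/1.0625 = 0.059. One non-opener in six is 0.167.

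**Step 3. Power at n=6 if some subjects do not open.** Assumptions: openers are normal with mean 200 and SD 50, and non-openers are exactly 0. With opening rate p, the mean is 200p and the variance is p × 50² + p(1 − p) × 200². At p = 0.75 the mean is 150, the variance is 1,875 + 7,500 = 9,375 and the SD is 96.8.

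| True opening rate | Mean (mm³) | SD (mm³) | Two-sided power, n=6 (simulated) |
|---|---|---|---|
| 100% | 200 | 50.0 | above 0.999 |
| 90% | 180 | 76.5 | 0.98 |
| 83% (5/6) | 167 | 87.4 | 0.93 |
| 75% | 150 | 96.8 | 0.82 |

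At 75%, the noncentral t with mean 150 and SD 96.8 gives 0.855. The simulation (1,000,000 trials) is the better guide, because the mixture is not normal. One-sided, the simulated power at 75% is 0.95.

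**Step 4. Check of the 0.82.** Simulated two-sided power, given the number who open, is about 1 with six or five openers, 0.978 with four and about 0 with three. The binomial probabilities at p = 0.75 are 0.178, 0.356, 0.297 and 0.132. So power = 0.178 + 0.356 + 0.297 × 0.978 = 0.824.

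**Step 5. What drives the fall.** If the SD rises to 96.8 but the mean stays at 200, power at n=6 is 0.978. The fall to 0.82 needs the lower mean as well.

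**The case against.** The strongest reply is that the 75% is a bar for the observed result and not a planning assumption. The planning evidence in sections 1.5.1 and 2.2 is opening in all animals, and inputs that suppose universal opening fit it. This stands. A reader might infer that the SD contradicts the 75% criterion. The documents do not support that: a study may be planned on universal opening and still set a lower bar for success.

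The second reply is that the t-test is not at risk when the success rule is met. This also stands. With five of six open, power is essentially 1. It collapses only at three or fewer, when the 75% rule has already failed and the three-failure provision in section 8.5 applies. At a true rate of 75%, the success rule itself is met with probability only 0.178 + 0.356 = 0.53, so the t-test is not the weaker criterion.

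The third reply is that 0.82 depends on choices the plan does not make: a two-sided test, non-openers at exactly zero and normally distributed openers. That is correct, and it is why the values should be labelled as sensitivity figures.

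A reader might also infer that only subjects whose barrier opened are to be tested. The comparison is described as being made for each patient, and section 7.3 selects on receipt of the device and compliance, not on opening. Nothing says that non-openers are dropped. A clarifying sentence is useful, but the text does not establish selection on the outcome.

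None of these replies rescues the stated 0.95, which the named test does not give at n=6 with the stated inputs.

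**Conclusion.** Two things hold. First, power 0.95 with six subjects does not follow from a paired t-test with difference 200 and SD 50 mm³. Two-sided power is above 0.999, and four subjects suffice for 0.95. This rests only on the plan's inputs and does not depend on sidedness or on which of the two SD readings is taken. Second, those inputs leave room for at most about 6% of subjects at 0 mm³, so the statement says nothing about power when some subjects do not open, which the plan foresees.

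The values of 0.98, 0.93 and 0.82 rest on the assumptions in step 3. It would be too strong to say that the study has power 0.82 instead of 0.95, because 75% is not an assumed rate and 0.95 is not what the inputs deliver. Nor do the figures show that six subjects are too few. Eight would be needed for two-sided power 0.95 at a true rate of 75% (0.92 at n=7, 0.97 at n=8), but the plan nowhere commits to that power at that rate. In a six-subject feasibility study judged on the proportion opened, this is a correction to a stated design property and not a threat to the design.

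**What to change.** In section 7.1:

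1. Replace the single power figure with power for the paired t-test at n=6 at stated opening rates. Under the assumptions above and two-sided alpha 0.05, these are above 0.999 at 100%, 0.98 at 90%, 0.93 at 83% and 0.82 at 75%. Label them as sensitivity values and state the assumptions.
2. State whether the test is one- or two-sided. If one-sided is chosen, recompute every value; the one at 75% becomes about 0.95.
3. State where the 50 mm³ comes from, whether it is the SD of the paired difference, and whether it describes openers or all treated subjects.
4. Confirm that every sonicated subject enters the volume analysis with the measured volume, 0 mm³ where there is no opening, and make section 7.3 agree. This is mainly clarification.

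Keep six subjects and the 75% success rule.

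The cost is a few sentences, with no added patients and no change to procedures. The downside is that the stated power is less favourable at lower opening rates.

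### Section 7.1: the stated inputs for the paired t-test do not make six the minimum number of subjects; with 50 mm³ as the SD of the differences, the minimum at two-sided alpha 0.05 is four

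*Combined protocol and SAP*

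**What the plan says.** Section 7.1 compares scans within each patient: "The scan with the BBB opening will be compared to the scan before BBB opening for each patient". It names the test: "The data will be statistically analyzed with parametric paired Student's t-test". The inputs are a "detectable difference of 200 mm³ (after BBB opening - before BBB opening") and "a standard deviation of 50 mm³". The result is that "at least 6 subjects are needed to report a result at the level of α =0.05 and Power=0.95".

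The section does not say whether the test is one- or two-sided, whether 50 mm³ describes the paired differences or a single scan, or where the 200 and 50 mm³ come from. It makes no allowance for dropout.

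Section 7.2 again expects a paired t-test but leaves room for non-parametric tests. Section 5.3 describes a single-arm trial, and sections 3.1 and 6 plan six patients.

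**The concern.** The planned difference is four times the SD. With an effect that large, a paired t-test needs very few pairs, so a minimum of six at 95% power looks too high.

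This sentence is the plan's only numerical justification for its size. An IRB or FDA reader would take six as the statistical floor and would conclude that losing one patient drops power below 0.95. On the stated inputs that is untrue. The reader is also not told how much larger the SD could be before six subjects stop being enough. That matters because no source is given for the 50 mm³. Section 8.5 foresees a possible request to FDA for more subjects, and such a request should start from a calculation that can be reproduced.

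**Working it through.** **Inputs.** From section 7.1: difference 200 mm³, SD 50 mm³, alpha 0.05, target power 0.95, paired t-test, stated minimum 6. Sidedness and the type of SD are not stated, so each option is tried.

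**Method.** Exact power from the noncentral t distribution with n − 1 degrees of freedom and noncentrality (200 / SD of differences) × √n.

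**Reading A: 50 mm³ is the SD of the paired differences.** The standardised effect is 200/50 = 4. The noncentrality is 4 × √3 = 6.93 at n=3, 4 × √4 = 8 at n=4 and 4 × √6 = 9.80 at n=6.

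**Reading B: 50 mm³ is the SD of each scan, with correlation ρ between the two scans.** The SD of the differences is 50 × √(2(1 − ρ)). At ρ = 0 this is 70.7 mm³, and the standardised effect is 200/70.7 = 2.83.

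| n | A, two-sided | A, one-sided | B (ρ = 0), two-sided | B (ρ = 0), one-sided |
|---|---|---|---|---|
| 3 | 0.908 | 0.991 | 0.705 | 0.908 |
| 4 | 0.998 | >0.999 | 0.9502 | 0.993 |
| 5 | 0.99999 | >0.999 | 0.995 | 0.9996 |
| 6 | >0.999 | >0.999 | 0.9996 | >0.999 |

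The smallest n with power of at least 0.95 is 4 in every column except A one-sided, where it is 3. Positive correlation between a patient's scans raises the figures in B. At ρ = 0.5 the SD of the differences is 50 × √1 = 50, and B becomes A. Simulation with 400,000 runs for A, two-sided, gave 0.909 at n=3 and 0.998 at n=4.

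**What would make six the minimum.** Two-sided, n=5 reaches 0.95 up to an SD of the differences of 90.75 mm³, and n=6 up to 107.1 mm³. Six is therefore the minimum only if the SD of the differences lies between about 91 and 107 mm³. With a per-scan SD of 50, the lower end requires 1 − ρ = (90.75/50)² / 2 = 1.647, so ρ is about −0.65 or lower. At ρ = −1 the SD of the differences is 100, and power is 0.909 at n=5 and 0.9705 at n=6.

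**What six subjects deliver.** Power 0.95 at n=6, two-sided, requires a standardised effect of 1.867. For a 200 mm³ difference the SD of the differences may rise to 200/1.867 = 107 mm³. At SD 50 the difference may fall to 1.867 × 50 = 93 mm³.

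**The non-parametric option.** The smallest two-sided p of an exact signed-rank test is 2/2ⁿ: 0.0625 at n=5 and 0.031 at n=6.

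**The case against.** **The 0.95 is a target.** A reader might infer that the plan also misstates achieved power, by about 5 points. The sentence is more naturally read as solving for n at a target of 0.95. On that reading only the minimum is wrong, and this point is confined to the minimum.

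**Six can be obtained from a paired test.** It can, with an SD of the differences of 100 mm³. That needs a strongly negative correlation between a patient's two scans, or the two SDs simply added. Section 7.1 supports neither.

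**Six is a real floor for a permitted analysis.** A two-sided signed-rank test cannot reach p<0.05 with fewer than six pairs, and section 7.2 would allow that test. This stands as a reason not to cut enrolment. It does not rescue section 7.1, which bases its calculation on the t-test and does not offer this reason.

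**The figure may come from an unpaired test.** A reader might infer this because three scans per group, six in total, give two-sided power of 0.948. The documents do not support it. Sections 7.1 and 7.2 both name a paired test, and section 5.3 describes a single arm. The 0.948 also falls short of 0.95, so solving for at least 0.95 would return four per group (0.996), or eight in total. The origin of the six is unknown.

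**The consequence is small.** This largely stands. The error is conservative, and section 7.1 defines success as safe opening in at least 75% of cases, not as a significant t-test.

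**Conclusion.** The claim that at least six subjects are needed is wrong for the stated inputs. With 50 mm³ as the SD of the paired differences, the minimum is four two-sided and three one-sided. With 50 mm³ as a per-scan SD and uncorrelated scans, four is still enough two-sided, but only just (0.9502). Six subjects exceed 0.999 under all of these readings.

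The figures assume normally distributed differences, no dropout, alpha 0.05 and, under the per-scan reading, a correlation that is not negative.

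A reader might infer that the trial should enrol four. That does not follow: the SD has no stated source, four pairs leave almost no margin under the per-scan reading, and the signed-rank test needs six. What needs correcting is the reported justification; the number enrolled can stay.

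**What to change.** In section 7.1:

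- Delete the statement that at least six subjects are needed.
- State whether the test is one- or two-sided.
- State whether 50 mm³ is the SD of the paired differences or of a single scan, and give its source.
- Report what six subjects deliver. If the test is two-sided, this could read: on the stated inputs, six subjects give power above 0.999 for the paired t-test, and power stays at or above 0.95 for a 200 mm³ difference up to an SD of the differences of about 107 mm³.
- Give the sponsor's own reason for choosing six. The documents call this an initial safety and feasibility study but do not say why the number is six, so the reason has to come from the sponsor.

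The cost is a few sentences in one section. Enrolment, procedures and the success criterion do not change.
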